7.6.3 Standard Biopsy Procedures

7.6.3.1 Local anesthetic: topical anesthesia consisting of viscous lidocaine, or topical application of 20% benzocaine, will be initially applied, and then the biopsy site will be injected with 1 or 2% lidocaine with or without 1:1000,000 epinephrine.

7.6.3.2 Incisional biopsy:

Lesion Biopsy

- For the baseline biopsy, using a Baker 4 mm punch, the center or clinically most suspicious area of the lesion is biopsied with a twisting motion. The circular punched out tissue is grasped gently with fine toothed forceps and excised just deep to the submucosa with the #15 scalpel. Care is taken to avoid collecting significant amounts of fat or muscle and to avoid crushing the specimen.
- Biopsy sample is placed mucosa side up on a clean hard surface such as a piece of wax paper, Whatman filter paper, or equivalent.
- The specimen will be oriented on the Whatman paper to further reduce artifact and preserve orientation. The specimen will be sent to the institutional pathology lab in 10% formalin (see section 10.2) for paraffin embedding, routine histopathology and stored for biomarker analyses.
- The above collection procedure will be utilized in an identical fashion for the post-treatment biopsy. The biopsy will be obtained from the most suspicious part of the lesion adjacent to the baseline biopsy. If no lesion persists post-treatment, then the biopsy will be taken from the site adjacent to the original biopsy.

Biopsy of visually normal cheek mucosa

A 3 mm punch biopsy will be collected from visually normal cheek mucosa in the similar fashion as the lesion biopsy.

7.6.3.3 Hemostasis is achieved by either direct pressure or suture, or silver nitrate stick.

7.6.3.4 Participants are provided with oral wound care instructions: 4-6 times daily local rinsing with saline and standard post surgical instructions including notification of consulting professional for heavy bleeding, severe pain, or fever.

7.6.3.5 For analgesia, participants will be told to take acetaminophen 325-650 mg po qid PRN. However, it is anticipated that the participants will not require significant pain control after the above procedure. Care should be taken to avoid Stenson's duct by greater than 1 cm after it is identified.

7.6.4 Saliva Collection

The collection of unstimulated whole saliva will be conducted as described below:

The patient should not have eaten for 90 minutes prior to the collection procedure. Saliva should be collected between 8 am and 12 noon, if feasible. During the collection period, the subject shall be

seated straight up with eyes open and head tilted slightly forward. The subject will be instructed to minimize oro-facial movements to minimize influence on salivary flow (the subject should not swallow and should not speak during the collection process). Immediately before the collection begins, the subject is instructed to swallow. The patient allows the saliva to accumulate in the floor of the mouth for 60 seconds without swallowing. The patient empties the entire accumulated saliva into the pre-weighed container, a 50 ml Falcon tube. The procedure is then repeated 4 more times for a total collection time of 5 minutes. Subjects are instructed not to swallow during the entire 5-minute collection period.

8. CRITERIA FOR EVALUATION AND ENDPOINT DEFINITION

8.1 Primary Endpoint

The primary endpoint is to determine whether 12-14 weeks of metformin intervention would improve the clinical response of oral premalignant lesions. Subjects who show complete or partial clinical response following the metformin intervention will be considered clinical responders.

Clinical response will be evaluated by the following criteria [50]:

Complete Response (CR): Disappearance of all evidence of lesion(s).

Partial Response (PR): Greater than or equal to 50% reduction in the sum of the products of diameters of lesion(s) measurable at baseline. Non-measurable lesion(s) may not increase greater than or equal to 25% in size and no new lesion may appear.

No Change (NC): No change in the size of the lesion(s) identified at baseline and no new lesions appearing, i.e., anything that is not CR, PR, or PD.

Progressive Disease (PD): Any increase greater than or equal to 25% in the product of the diameters of any lesion(s) measurable at baseline or in the estimated size of lesion(s) non-measurable at baseline or the appearance of an unequivocal new lesion.

8.2 Secondary Endpoints (in order of priority)

8.2.1 Histologic response to metformin intervention in the target lesion

Histologic response will be evaluated by the following criteria:

Complete Response (CR): Complete reversal of dysplasia or hyperplasia to normal epithelium in the target lesion.

Partial Response (PR): Improvement of the degree of dysplasia or hyperplasia in the target lesion.

No Change (NC): No change in the degree of dysplasia or hyperplasia in the target lesion, anything that is not CR, PR or PD.

Progressive Disease (PD): Increase in the severity of grade of histology in the target lesion.

8.2.2 Tissue-based biomarkers

8.2.2.1 Metformin effect on cell proliferation and its molecular targets in the target lesion and in the normal tissue. The expression of the following markers will be assessed in the baseline and post-intervention biopsies.

8.2.2.1.1 Marker of cell proliferation, Ki67

8.2.2.1.2 Molecular targets of metformin, including, in order of priority, pS6, pAKT^{S473}, p4EBP, pACC

8.2.2.2 Expression of frequent dysregulated molecular mechanisms and organic cation transporter 3 (OCT 3) in the target lesion and in the normal tissue, including, in order of priority, EGFR, pEGFR, p53, PTEN, pERK, p16, and OCT3. The expression of these biomarkers will be assessed in the baseline

and post-intervention biopsies to determine the biochemical consequences of the metformin treatment, and their potential relationship with the clinical response to metformin.

- 8.2.2.3 Targeted analysis of cancer-associated genes in the target lesion and blood DNA collected at baseline to determine the impact of genomic alterations on the biological and biochemical consequences and clinical response to metformin.
- 8.2.3 Serum and saliva based biomarkers
 - 8.2.3.1 Metformin effect on serum metabolic markers (C-peptide, glucose and HbA1c)
 - 8.2.3.2 Metformin concentrations in serum and saliva at baseline and post-intervention
 - 8.2.3.3 Metformin effect on serum and saliva inflammatory and angiogenic cytokines, including interleukin (IL)-6, IL-8, growth-related oncogene-1 (GRO-1), and vascular endothelial growth factor (VEGF). These cytokines will be measured in samples collected at baseline and post-intervention.
- 8.2.4 Exploratory Endpoints
 - 8.2.4.1 To characterize changes in the saliva microbiome before and after metformin intervention, including both the absolute microbial load and taxonomic composition.
 - 8.2.4.2 To evaluate the potential microbiome signatures that are correlated with treatment response.

8.3 Off-Agent Criteria

Participants may stop taking study agent for the following reasons: completed the protocol-prescribed intervention, adverse event or serious adverse event, inadequate agent supply, noncompliance, concomitant medications, medical contraindication. Participants will continue to be followed, if possible, for safety reasons and in order to collect endpoint data according to the schedule of events.

8.4 Off-Study Criteria

Participants may go ‘off-study’ for the following reasons: the protocol intervention and any protocol-required follow-up period is completed, adverse event/serious adverse event, lost to follow-up, non-compliance, concomitant medication, medical contraindication, withdraw consent, death, determination of ineligibility (including screen failure).

8.5 Study Termination

NCI, DCP as the study sponsor, and the FDA have the right to discontinue the study at any time.

9. CORRELATIVE/SPECIAL STUDIES

9.1 Rationale for Methodology Selection

Tissue biomarkers, including Ki67, pS6, pAKT^{S473}, p4EBP, pACC, EGFR, pEGFR, p53, PTEN, pERK, p16, and OCT3 will be assessed by immunohistochemistry (IHC). IHC is the best and most validated

technique for measuring protein levels of the biomarkers of interest in paraffin-embedded tissue. It allows analyses of relative expression levels of each biomarker and determination of localization of each marker.

Serum and saliva metformin concentrations will be determined by chromatography-tandem mass spectrometry method, which provides high sensitivity and specificity for metformin analysis.

Serum and saliva inflammatory and angiogenic cytokines, including IL-6, IL-8, GRO-1, and VEGF, will be measured by Luminex Multianalyte System. Luminex™ technology allows for simultaneous quantification of multiple proteins in a single sample.

Genomic analyses will be conducted in blood DNA and DNA extracted from the target lesion by targeted sequencing using the current Expanded Solid Tumor Panel at the Center for Advanced Laboratory Medicine, University of California San Diego. This panel covers all exons for 399 genes, which is designed to detect hotspot mutations and key fusion of approximately 400 genes often associated with cancer progression, including oral cancer. Importantly, targeted sequencing has been applied successfully to DNA extracted from formalin-fixed paraffin-embedding tissue sections.

The microbial load in the saliva samples will be determined using the flow cytometry method described by Vandeputte et al. [51]. Samples are first diluted ten-fold in sterile saline solution, then filtered across a 5 µm filter to dissociate aggregates and remove human epithelial cells. The sample is then stained with SYBR green, a cell membrane permeable fluorescent DNA stain. Populations with increased intensity specific to SYBR green fluorescence above a stained vehicle control are enumerated with counting beads to extrapolate the number of microbial cells per mL of original sample. By using serially diluted saliva samples, we have shown that we can reproducibly detect the microbial load across a 1,000-fold range of dilutions. The total number of microbial cells per mL of human saliva can then be used to normalize the sequencing results to represent the number of bacterial taxa per mL instead of compositional data that only identifies the ratio of microbes. In preliminary experiments with healthy individuals, we found a 100-fold difference in microbial load per mL of saliva. This dramatic difference would have a large impact on interpretation of microbial sequencing results from saliva, and accounting for this variability in our clinical cohort will improve our ability to detect meaningful changes.

For shotgun metagenomic sequencing, DNA will be extracted in triplicate from 200 µl aliquots of frozen, unstimulated saliva using our high-throughput, automated DNA extraction pipeline [52]. Next, 5 ng of each aliquot of extracted DNA will be used to create shotgun metagenomic libraries with the Kapa HyperPlus kit. We have established an automated, miniaturized shotgun metagenomics library preparation pipeline, where we can readily process 384 samples at one-tenth the volume and a fraction of the cost within a single day. Importantly, we have also recently optimized a method to reduce the amount of human DNA from saliva samples for improved microbial assessment [53]. Sequencing data will be processed as previously described [53]. Briefly, demultiplexed samples will be trimmed and quality filtered using Atropos v 1.1.5, a fork of Cutadapt. Reads aligning to the host genome will be identified using Bowtie 2 v2.3.0 and filtered from downstream analysis. The host-filtered microbial reads will be profiled using MetaPhlAn v2.0 and the taxonomic output matrix will be filtered to represent only the relative abundance of the most specific taxonomic level. We will normalize the resulting matrix to account for differences in microbial load as described by Vandeputte et al. Bray-Curtis and Binary Jaccard beta diversity analysis will be performed using QIIME2 to visualize the impact of metformin on the salivary microbiome.

9.2 Comparable Methods

Proposed methods are standard methodologies used in other research studies. The resulting data will be able to be compared to existing data.

10. SPECIMEN MANAGEMENT

10.1 Laboratories

Clinical chemistry, hematology, C-peptide, and HbA1c will be performed at the institutional or commercial diagnostic laboratories.

Immunohistochemistry will be performed in the laboratory of [name] at UCSD.

Serum and saliva cytokine markers will be performed at the University of Maryland Cytokine Core Laboratory.

Genomic analysis will be performed at the UCSD Center for Advanced Laboratory Medicine.

Serum and saliva metformin concentrations will be determined in the University of Arizona Cancer Center Analytical Chemistry Shared Resource led by [name].

10.2 Collection and Handling Procedures

Baseline

Ten milliliters of fasting blood (1 x 7 ml SST tube; 1 x 3 ml Lavender-EDTA tube) will be collected at Baseline for CBC with diff, CMP, HbA1c, and C-peptide. SST tubes will be held at room temperature for 30 min followed by centrifugation. Lavender-EDTA tube will be inverted gently 5 times. Both will be prepped, labeled, and packaged according to the recommendation from the diagnostic lab. These samples will be sent immediately for analysis.

The lesion biopsy will be placed in a standard pathology container for tissue fixation in 10% formalin and labeled according to the requirements from the pathology lab. Biopsy of normal mucosa will be placed in a standard pathology container for tissue fixation in 10% formalin and labelled according to the requirements from the pathology lab.

Ten milliliters of fasting blood will be collected at Baseline for research biomarkers (1 x 7 ml SST tube; 1 x 3 ml Lavender-EDTA tube for serum markers and genome analysis, respectively). SST tubes will be held at room temperature for 30 min followed by centrifugation. Serum will be aliquoted evenly into 10 x 1 ml cryovials. Lavender-EDTA tube will be inverted gently 5 times. Cryovials and Lavender-EDTA tubes will be labeled with the study ID, participant ID, and visit type (baseline). Samples will be stored at -80°C prior to analysis.

Saliva will be collected into a 50 ml conical tube for cytokine markers. Saliva will be aliquoted evenly into 10 x 1 ml cryovials. Cryovials will be labeled with the study ID, participant ID, and visit type (baseline). Samples will be stored at -80°C prior to analysis.

Post-Intervention

Ten milliliters of fasting blood (1 x 7 ml SST tube; 1 x 3 ml Lavender-EDTA tube) will be collected at post-intervention for CBC with diff, CMP, HbA1c, and C-peptide. SST tubes will be held at room temperature for 30 min followed by centrifugation. Lavender-EDTA tube will be inverted gently 5 times. Both will be prepped, labeled, and packaged according to the recommendation from the diagnostic lab. These samples will be sent immediately for analysis.

The lesion biopsy will be placed in a standard pathology container for tissue fixation in 10% formalin and labelled according to the requirements from the pathology lab. Biopsy of normal mucosa will be placed in a

standard pathology container for tissue fixation in 10% formalin and labelled according to the requirements from the pathology lab.

Seven milliliters of fasting blood will be collected at post-intervention for research biomarkers (1 x 7 ml SST tube for serum markers). SST tubes will be held at room temperature for 30 min followed by centrifugation. Serum will be aliquoted evenly into 10 x 1 ml cryovials. Cryovials will be labeled with the study ID, participant ID, and visit type (post). Samples will be stored at -80°C prior to analysis.

Saliva will be collected into a 50 ml conical tube for cytokine markers. Saliva will be aliquoted evenly into 10 x 1 ml cryovials. Cryovials will be labeled with the study ID, participant ID, and visit type (post). Samples will be stored at -80°C prior to analysis.

Twelve to fifteen formalin-fixed paraffin-embedded unstained tissue sections (4 µm) from biopsy collected at baseline and post-intervention will be requested from each institution's pathology department for measurement of tissue biomarkers.

Centralized pathology review

Centralized pathology review will occur for eligibility assessment and after study completion. The H&E stained section of the target lesion biopsy will be scanned by study personnel at each site using Aperio or equivalent scanner. [name] at UCSD will perform an independent centralized pathology review of the scanned slides.

In case of disagreement between the local site and central path review conducted by [name], the following actions will take place:

1. For minor discrepancy (one level change) in diagnoses, [name] evaluation will be considered final, for consistency.
2. For major discrepancy (two levels or more difference), the case will be referred to [name] at the NCI for independent review. The consensus evaluation of two pathologists in agreement will be used as the final diagnosis.
3. For disagreement among all three pathologists (local site, [name], and [name]), [name] and [name] will discuss the case and come to a consensus.

A designated UCSD site coordinator will be trained to compare the review from the local pathologist with the central pathology review and ensure timely notification to the site that the participant is eligible.

10.4 Tissue Banking

Biologic specimens collected during the conduct of each clinical trial that are not used during the course of the study will be considered deliverables under the contract and thus the property of the NCI. At study completion, NCI reserves the option to either retain or relinquish ownership of the unused biologic specimens. If NCI retains ownership of specimens, the Contractor shall collect, verify and transfer the requested biologic specimens from the site to a NCI-specified repository or laboratory at NCI's expense. The specimens will be made available to the research community. Specimens sent to researchers will be coded such that participant identity will be protected.

In concordance with the NCI Genomic Data Sharing Policy, genomic data generated in this study will be deposited in dbGaP and will be available in a controlled-access manner.

11. REPORTING ADVERSE EVENTS

DEFINITION: AE means any untoward medical occurrence associated with the use of a drug in humans, whether or not considered drug related. An AE can therefore be any unfavorable and unintended sign), symptom, or disease temporally associated with participation in a study, whether or not related to that participation. This includes all deaths that occur while a participant is on a study.

Please note that all abnormal clinical laboratory values that are determined to be of clinical significance based on a physician's assessment are to be reported as AEs. Those labs determined to be of no clinical significance or of unknown clinical significance (per the physician's assessment) should not be reported as AEs. Any lab value of unknown clinical significance should continue to be investigated/followed-up further for a final determination, if possible.

A list of AEs that have occurred or might occur (Reported Adverse Events and Potential Risks) can be found in §6.2, Pharmaceutical Information, as well as the Investigator Brochure or package insert.

11.1 Adverse Events

11.1.1 Reportable AEs

All AEs that occur after the informed consent is signed and baseline assessments are completed (including run-in) must be recorded on the AE CRC (paper and/or electronic) whether or not related to study agent.

11.1.2 AE Data Elements:

The following data elements are required for adverse event reporting.

- AE verbatim term
- System Organ Class (SOC)
- Common Terminology Criteria for Adverse Events v4.0 (CTCAE) AE term
- Event onset date and event ended date
- Severity grade
- Attribution to study agent (relatedness)
- Whether or not the event was reported as a serious adverse event (SAE)
- Whether or not the subject dropped due to the event
- Outcome of the event

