7. CLINICAL EVALUATIONS AND PROCEDURES

7.1 Schedule of Events

Evaluation/ Procedure ¹	Baseline	Agent Start Day 1 of Week 1	Weeks 1-5	Week 6 (± 1 week)	Weeks 7-11	Week 12-14 or Early Termination	Follow-Up (2-4 weeks post- intervention)
Informed Consent	X						
Assess Eligibility	X						
Medical History	X			X		X	
Vital Signs ² / Height ³ and Weight	X			X		X	
Physical Exam ⁸	X			X		X	
Performance status	X						
Concomitant medications	X		X	X	X	X	X
Assessment of tobacco and alcohol use	X					X	
Fasting blood for CBC/diff, CMP ⁷ , C- peptide, HbA1c	X					X	
Urine pregnancy test if applicable	X	X ⁴		X		X	
Examination of oral cavity	X			X		X	
Lesion measurement	X			X		X	
Photography	X			X		X	
Biopsies ⁵	X					X	
Saliva collection for research biomarkers ¹⁰	X					X	
Fasting blood collection for research biomarkers	X					X	
Dispense Study Agent ⁴		X		X			
Collect Study Agent				X		X	
Review Agent Diary/Record				X		X	
Adverse Events			X	X	X	X	X
Telephone/Email Contact			X ⁶		X ⁹		X

¹ Initiation of study agent should occur within 9 weeks of baseline biopsy. On-study evaluations should be conducted with the following timeframes: week 6 interim visit can be scheduled +/- 1 week; total agent intervention duration is 12 – 14 weeks; post-intervention visit can be scheduled between weeks 12-14; the agent should be taken until the evening before the post-intervention visit.

² Vital signs include temperature, blood pressure, and pulse.

³ Only at baseline.

⁴ Eligible participants may have agent shipped to them. Urine pregnancy test for women of childbearing potential does not need to be repeated at agent start if the baseline test was done within 4 weeks prior to agent start.

⁵ At baseline, a biopsy will be performed on the lesion that meets the size criteria or on the largest lesion, if multiple lesions that meet the size criteria. If smaller lesions meet the size criteria and are of clinical concern to treating physician, they may be biopsied. The lesion with the worst histology following the central pathology review will be the target lesion and re-biopsied at post-intervention. If the target lesion is not visible post-intervention, a biopsy will be obtained at the site of the previous lesion biopsy. Biopsy of visually normal cheek mucosa will be obtained at baseline and post-intervention.

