Biopsy of visually normal cheek mucosa will be performed on all participants to evaluate tissue markers, including those who had a prior lesion biopsy that is qualifying.

Saliva will be collected for metformin levels and cytokine biomarkers. Saliva should be collected between 8 am and 12 noon, if feasible.

Fasting blood will be collected for complete blood count with differential (CBC-diff), comprehensive metabolic panel (CMP), C-peptide, and HbA1c. Fasting blood will also be collected for serum metformin levels, serum cytokine biomarkers, and genomic analysis of blood DNA.

Urine pregnancy test will be performed for potentially fertile women.

Participants may return within 7 days of the Baseline Testing/Pre-Study Visit for procedures not performed during the Baseline Testing/Pre-Study Visit. Participants will be provided with an AE Diary and instructions on how to complete the AE Diary.

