7.4 Evaluation at Completion of Study Intervention

Participants will return after 12-14 weeks of agent intervention for post-intervention evaluation. This visit should be scheduled between 8 am and 12 noon because of the saliva collection. During this visit, participants will return unused pills and be evaluated for weight, vital signs, AEs, concomitant medications, and tobacco and alcohol assessment. They will undergo a brief physical assessment of the chest, heart, abdomen, and lower extremities for pedal edema and be assessed for changes in medical history. The tobacco and alcohol history will be recorded directly onto the CRF which will be considered the source document for these data.

Participants will undergo an oral exam for lesion measurement and photography. Bi-dimensional measurements for all lesions will be recorded. Lesions that do not meet the size criteria ($<8 \times 3$ mm) will be measured but recorded as non-measurable. Color photographs of all lesions will be taken.

A biopsy will be performed on the selected target lesion for histopathology and tissue markers. If the target lesion is not visible post-intervention, a biopsy will be obtained at the site of the previous lesion biopsy. A biopsy of visually normal cheek mucosa will be performed for tissue markers.

Saliva will be collected for metformin levels and cytokine biomarkers.

Fasting blood will be collected for complete blood count with differential (CBC-diff), comprehensive metabolic panel (CMP), C-peptide, and HbA1c. Fasting blood will also be collected for serum trough metformin levels and serum cytokine biomarkers. Urine pregnancy test will be repeated, if indicated.

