7.5 Post-intervention Follow-up Period

Participants will be contacted by telephone (or email) 2-4 weeks later for a final AE assessment of drug, and to be provided with final biopsy report. Participants will be reminded to return the AE Diary to the study office in a pre-stamped envelope.

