11.1.4 Assessment of relationship of AE to treatment

The possibility that the adverse event is related to study agent will be classified as one of the following: not related, unlikely, possible, probable, definite.

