13.7 Evaluation of Toxicity

All participants will be evaluable for toxicity from the time of their first dose of drug. Descriptive statistics of the type and frequency of all adverse events will be generated, including 95% confidence intervals.

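### AE recording starts only once baseline assessments are complete, so events during the baseline biopsies need not be recorded

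*Combined protocol and SAP*

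**What the plan says.** Section 11.1.1 sets the start of recording: "All AEs that occur after the informed consent is signed and baseline assessments are completed (including run-in) must be recorded". Two conditions are joined, consent and completion of baseline. Once both are met, the duty applies regardless of any relation to the agent.

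The biopsies belong to baseline. Footnote 5 of the schedule in 7.1 says "At baseline, a biopsy will be performed on the lesion that meets the size criteria or on the largest lesion" where several qualify, and "Biopsy of visually normal cheek mucosa will be obtained at baseline and post-intervention". Section 7.6.3 describes topical and injected anesthetic, a 4 mm punch for the lesion and a 3 mm punch for the cheek. If a qualifying lesion biopsy was taken in the preceding 6 weeks, archival tissue replaces the lesion punch, but the cheek punch is still done. Baseline need not be a single day: "Participants may return within 7 days of the Baseline Testing/Pre-Study Visit for procedures not performed" at that visit (7.2).

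The other relevant places are these:

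- **7.1:** the Adverse Events row is empty at Baseline and at Agent Start. Its first mark is in the Weeks 1-5 column.
- **11.1.4:** "The possibility that the adverse event is related to study agent will be classified as one of the following", followed by five levels. Neither this section nor the data elements in 11.1.2 offer attribution to a study procedure.
- **13.7:** "All participants will be evaluable for toxicity from the time of their first dose of drug". The next sentence promises descriptive statistics for all adverse events.
- **7.4 and 7.5:** after treatment, "A biopsy will be performed on the selected target lesion for histopathology and tissue markers" and the cheek punch is repeated. Participants are then "contacted by telephone (or email) 2-4 weeks later for a final AE assessment of drug".
- **11.2:** defines SAEs and sets reporting times, but gives no date from which the duty runs.

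**The concern.** The rule opens the record only after the procedures most likely to cause an event before dosing have been done. Section 7.6.3 itself foresees complications: its wound-care instructions ask participants to report heavy bleeding, severe pain or fever. The cheek punch is taken from healthy mucosa for tissue markers alone, so a participant gains nothing from it clinically. A trial should be able to count the harms of such a procedure.

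The same punches after treatment fall inside the recording window and are followed by an AE contact. Procedure harms are therefore collected more fully after drug than before it, in a trial with no control arm. With attribution limited to the agent, a complication of the post-treatment biopsy has no field that marks it as due to the biopsy. What is at stake is the safety record. The efficacy analysis is not affected.

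**Working it through.** The plan states no biopsy total and no expected number of procedure-related events, so there is no figure of its own to reproduce on this point. The check is mainly a comparison of sections, with a count to show scope.

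**1. Order of events under the plan**

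1. Consent, which is also registration (6.8).
2. Baseline visit: oral examination, anesthetic, lesion punch, cheek punch, blood, saliva (7.2, 7.6.3).
3. Possible return visit within 7 days for procedures not yet done (7.2).
4. Baseline complete: the 11.1.1 window opens here.
5. Central pathology review settles histologic eligibility (7.2, 10.2).
6. Agent start, up to 9 weeks after the baseline biopsy (7.1, 7.3).
7. First AE mark in the schedule, Weeks 1-5 (7.1).

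**2. Length of the excluded period**

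- Single-day baseline: the procedures themselves and the rest of that visit's assessments.
- Split baseline, biopsy at the first visit: from the biopsy to the last deferred procedure, up to 7 days.
- Split baseline, biopsy deferred to the end: essentially the biopsy itself.

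The interval of up to 9 weeks before dosing is not excluded. It has no AE mark in the schedule, but 11.1.1 already covers it.

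**3. Does another section set an earlier start?**

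| Section | Content | Earlier start? |
|---|---|---|
| 7.1 | AE row blank at Baseline and Agent Start | No |
| 7.2 | AE Diary and instructions given at baseline | No start rule; may capture events |
| 7.3 | Telephone or email contact before agent start | After baseline is complete; aimed at dosing suitability |
| 11.2 | SAE definition and reporting times | No start date |
| 13.7 | Toxicity from first dose; all AEs described | Uses what was recorded |

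By contrast, 5.5 asks that medicines taken for a biopsy be logged, and 7.1 marks concomitant medications at Baseline. The plan thus has a place for biopsy drugs at that visit but not for biopsy events.

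**4. Procedures touched (scope, not events missed)**

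Inputs: 26 participants starting agent and at least 20 completing (13.3); by default 2 punches at baseline and 2 after treatment (7.1, 7.4).

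- Baseline punches: 2 × 26 = 52, of which 26 are cheek punches.
- Default share of scheduled punches: 52 / (52 + 2 × 26) = 52/104 = 50%.
- All baseline lesion tissue archival: 26 / (26 + 52) = 26/78 = 33%.
- 20 completers, no biopsies at early termination, no archival tissue: 52 / (52 + 40) = 52/92 = 56.5%.
- Assuming 10 biopsied screen failures (the documents give no number), full completion and no archival tissue: (52 + 20) / (72 + 52) = 72/124 = 58%.

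Optional biopsies of further lesions would add to the baseline count.

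**5. Effect of the fix on the design**

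Rejecting at 10 or more responders of 20 gives exact alpha P(X ≥ 10 | 20, 0.30) = 0.0480 and power P(X ≥ 10 | 20, 0.60) = 0.8725, which reproduces the 87% in 13.4. None of these inputs depends on when AE recording starts.

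**The case against.** The strongest reply is that the gap is small and partly covered. Bleeding, infection or pain that arises after baseline is complete must be recorded under 11.1.1 whatever its cause. The AE Diary is handed out at baseline and returned at the end, a contact takes place before agent start, and participants are told to report wound complications. All of this stands, and it confines the point to the procedures and any remainder of a split baseline.

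Five stronger readings are tempting, and the documents do not support them:

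- **Half of biopsy harms are lost.** The 50% is a share of scheduled punches. Nothing in the documents gives an event rate or says what fraction of events would arise inside the excluded period.
- **Serious baseline events fall outside reporting.** Section 11.2 carries no condition that baseline be complete. It is silent on a start date, which is a reason to state one, but it does not exclude such events.
- **11.1.1 contradicts the definition in Section 11.** A definition of what an AE is may be wider than the period in which AEs must be recorded.
- **13.7 discards events before dosing.** Only toxicity evaluability runs from first dose; the same section describes all adverse events.
- **Biopsied screen failures are exempt.** Section 11.1.1 is not limited to eligible or treated participants. The schedule shows no later contact for them, but their number is unknown, and the consent pages were not available for this review.

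It is also fair to say that the lesion biopsy serves eligibility, so only the cheek punch is purely for research. Counting agent toxicity from first dose is ordinary practice.

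**Conclusion.** The point holds in a limited form. A site that follows 11.1.1 to the letter need not record an AE that occurs during the baseline anesthetic and punches, or before a split baseline is finished. No other section sets an earlier start. The excluded period runs from the procedure itself to at most 7 days. By default it touches 2 punches per participant, or 1 where archival lesion tissue is used.

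This rests on reading the biopsies as baseline assessments, which 7.1 and 7.2 make plain, and on the available text holding no other start rule. How many events would be missed cannot be estimated from the documents. The change is best treated as a cheap improvement to safety recording rather than as the repair of an error, and it has no bearing on the primary analysis.

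**What to change.** - **11.1.1:** record AEs and SAEs from the first study-specific procedure after consent, and say that this includes biopsied participants who then fail screening. Saying so for SAEs also settles the start date that 11.2 leaves open.
- **7.1:** add an AE mark at Baseline and at Agent Start.
- **11.1.2 and 11.1.4:** add attribution to study procedure (biopsy) alongside attribution to agent, so that biopsy events can be separated from agent toxicity. Section 13.7 can go on counting agent toxicity from first dose.

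A dedicated contact for biopsied screen failures and a separate table of biopsy events would be useful extras, but the core change does not depend on them.

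The cost is a protocol amendment with the sponsor and IRB approvals that 14.3 requires, one CRF field, and slightly more AE data entry. Sample size, alpha and power stay as they are.
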